9.4 Study Assessments

9.4.1 Tumor Measurements:

Tumor measurements will be done at each visit. Imaging assessment with high frequency ultrasound will be done at baseline and at the second follow-up visit (Visit 6). At baseline, up to 5 TILs that are at least 10cm apart will be selected to be followed over the course of the study. Up to 10 TNILs can be followed with no more than 2 TNILs selected in the same anatomical area as a TIL. Responses in TILs and TNILs will be measured serially. Clinical measurements will be performed with a millimeter measuring tape (Appendix A). All measurements will be selected that will be able to be followed clinically and for ultrasound evaluations. The RECIST 1.1 (Appendix B) response criteria will be used to evaluate tumor response. Individual tumor measurements will also be conducted to determine clinical management of TILs and TNILs. The timeframe for the clinical (primary endpoint) and evaluation will be at Visit 6 and for high-frequency ultrasound (secondary endpoints) at Visit 6 as well.

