9.4.1.2 Clinical Management of TILs and TNILs

Along with assessing the overall tumor response (see Section 9.4.1.1, Tumor Response), each individual lesion will be assessed to determine appropriate clinical management. The RECIST 1.1 (Appendix B) response criteria will also be used to evaluate each individual tumor response.

Individual Lesion Complete Response (IL-CR): Complete disappearance of target lesion (whether measurable or not, and no new lesion(s) at the site of the target lesion) confirmation by an assessment 8 weeks after the end of the injections (Visit 6).

Individual Lesion Partial Response (IL-PR): Decrease in tumor burden $\ge 30\%$ relative to baseline confirmed by an assessment 8 weeks after the end of the injections (Visit 6).

Individual Lesion Progressive Disease (IL-PD): Progression is defined as >20% increase of at least 5 mm in the sum of the longest diameters of the target lesions or increase in tumor burden $\ge 20\%$ relative to nadir (minimum recorded tumor burden) or the appearance of one or more new lesions confirmed by an assessment 8 weeks after the end of the injections (Visit 6).

 Individual Lesion Rapid PD (IL-RPD): Is defined as an increase of >50% in tumor burden for lesions >2 cm in diameter or 100% tumor burden increase for lesion ≤2cm between visits.

Individual Lesion Stable Disease (IL-SD): Not meeting criteria for CR or PR, in

absence of PD (Decrease of tumor size <30% to increase in size <20% of less than 5 mm in the sum of the longest diameters of the target lesions).

	Individual Lesion	Individual	Progressive Disease	Stable Disease
	Complete Response	Lesion Partial	(PD)	(SD)
	(IL-CR)	Response (IL-		
	IL-CR to be	PR)		
	determined at the latest by Visit 6 (8	 IL-PR will be followed and assessed at 	 If IL-PD confirmed in two consecutive visits OR at Visit 6 (8 week 	 IL-SD will be followed and assessed up to
	week follow up), and will be followed for 6	assessed at Visit 6 (8 week follow up)	OR at Visit 6 (8 week follow up), TIL will be withdrawn and	assessed up to Visit 6 (8 week follow up)
	months • No additional	 If IL-SD is documented at 	alternative therapeutic intervention given	 Alternative therapeutic

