	 injections will be given to TILs who have achieved IL-CR prior to the 4th injection visit If recurrent at any 	Visit 6 or beyond, alternative therapeutic intervention will be offered	 If subject has additional TILs, will continue study participation If subject has only one, subject will be 	intervention will be offered if no IL-CR or IL-PR is observed by Visit 6.
TILs	point after IL-CR has been documented, then alternative therapeutic intervention offered (surgical excision, radiation, intralesional therapy etc.) based on patient preference	• If IL-PR continues, TIL will be closely followed until Visit 8, where alternative therapeutic intervention will then be offered	 withdrawn If IL-RPD occurs, treatment will be deferred that visit and will be reevaluated next visit. o If IL-PD confirmed, lesion withdrawn from study and alternative 	
			therapeutic intervention ○ If subject has more than one TIL, then lesions will continue to be a part of the study	
TNILs	 IL-CR to be determined at the latest by Visit 6 (8 week follow up), and will be followed for 6 	• IL-PR will be followed and assessed up to Visit 6 (8 week follow up)	 IL-PD at Visit 3 will undergo alternative therapeutic intervention 	 IL-SD will be followed and assessed up to Visit 6 (8 week follow up)
	monthsIf recurrent at any	 Alternative therapeutic 		 Alternative therapeutic

Table 7. Management of individual TILs and TNILs

point after IL-CR ha	s intervention will	intervention will
been documented a	It be offered if no	be offered if no
Visit 6, then	IL-CR is	IL-CR is
alternative	observed by	observed by
therapeutic	Visit 6	Visit 6
intervention offered		

9.4.2 High Resolution Ultrasonography of Squamous Cell Cancer:

The subjects will complete ultrasound assessments of their lesions at screening Visit (0), and at Visit 6 (second follow up visit).

METHOD:

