16. STATISTICAL CONSIDERATIONS

16.1 Analysis Endpoints

16.1.1 Primary Endpoint

The primary end point is to evaluate the overall response rate (ORR) defined as proportion of subjects who achieved CR and PR in the cSCC TILs. Clinical assessments will be done using a ruler or calipers. Digital photograph of the lesion(s) will be recorded each visit. Through clinical evaluation, CR will be defined as the complete disappearance of all TILs and PR will be defined as at least a 30% decrease in the sum of the diameters of TILs, taking as reference the baseline sum diameters. Progression is defined as >20% increase of at least 5 mm in the sum of the longest diameter recorded or increase in tumor burden \ge 20% relative to nadir (minimum recorded tumor burden) or the appearance of recurrent lesions confirmed by an assessment 8 weeks after the end of the injections (Visit 6). Stable disease (SD) is defined as decrease in tumor size <30% or an increase in size <20%.

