16.2 Statistical Analysis

Any patient who was treated with at least 1 dose of talimogene laherparepvec therapy will be included in safety and efficacy analysis. Descriptive statistics (mean, median, standard deviation, 25th percentile, 75th percentile, and range) will be presented for continuous variables, such as age. Frequency counts will be presented for categorical variables such as sex and race.

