16.2.1 Overall Response Rate (ORR)

The analysis of ORR will use a Simon two-stage optimum design to test that the proportion with ORR is \geq 80% (alternative hypothesis) versus ORR \leq 50% (null hypothesis). In the first stage, 7 patients will be recruited. If \leq 4 have ORR the trial will be terminated. If 5 or more have ORR, accrual will continue to the second stage. In the second stage, an additional 13 patients will be recruited. At the end of the second stage, if \geq 14 patients have ORR then TVEC will be considered promising for further study. This design yields 80% statistical power with a one-sided alpha level of 0.05.

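### No rule says how an injected lesion withdrawn for progression and given alternative therapeutic intervention enters the Visit 6 diameter sum that decides the primary endpoint

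*Combined protocol and SAP*

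**What the plan says.** Section 16.1.1 makes the primary endpoint the proportion of subjects with complete response (CR) or partial response (PR) in their TILs. PR is "at least a 30% decrease in the sum of the diameters of TILs, taking as reference the baseline sum diameters"; CR is the disappearance of all TILs. Section 9.4.1 fixes the time: "The timeframe for the clinical (primary endpoint) and evaluation will be at Visit 6". Section 16.2 fixes the population: "Any patient who was treated with at least 1 dose of talimogene laherparepvec therapy will be included in safety and efficacy analysis".

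Section 16.2.1 feeds the count into a Simon two-stage design. The trial stops at 4 or fewer responders of 7. If at least 14 of 20 "patients have ORR then TVEC will be considered promising for further study".

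Section 6.1 allows up to five TILs per subject, and Table 7 in Section 9.4.1.2 manages them one at a time. Its entry for a progressing TIL begins "If IL-PD confirmed in two consecutive visits", or at Visit 6, and continues "TIL will be withdrawn and", after which an alternative intervention is given. Then: "If subject has additional TILs, will continue study participation". A subject with a single TIL is withdrawn. The sub-entry on rapid progression reads "If IL-PD confirmed, lesion withdrawn from study and alternative", again followed by other treatment.

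None of Sections 9.4.1.1, 15, 16.1.1, 16.2 or Appendix B says what value a withdrawn TIL takes in later sums. Section 15 deals only with subjects who withdraw.

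**The concern.** Table 7 can remove a failed lesion from study follow-up well before the primary assessment, while the endpoint still needs a Visit 6 sum for that subject. Three treatments of the lesion are open:

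- measure the treated site as it stands, which may be 0 mm;
- drop the lesion from the baseline and Visit 6 sums;
- carry its last diameter forward.

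The first credits another therapy's effect to the study drug. The second removes the failure from view. Either can make the subject a responder where the third would not. A site cleared by another therapy could also be read as a lesion that has disappeared for CR.

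The stopping rule in Section 11.4 does not close the gap. It applies when 75% or more of a subject's TILs meet withdrawal criteria; one failed TIL of two (50%) or of three (33%) does not reach it. With 20 subjects and a single arm, one reclassified subject can decide stage 1 (5 versus 4 of 7) or the final result (14 versus 13 of 20).

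**Working it through.** **Timing.** The intervals in Table 1 put Visits 1 to 6 at weeks 0, 3, 5, 7, 11 and 15. Progression at two consecutive visits can first be confirmed at Visit 3 (week 5), 15 - 5 = 10 weeks before the primary assessment.

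**The plan's own figure.** Inputs from Section 16.2.1: n1 = 7, continue if at least 5 respond, N = 20, success if at least 14 respond.

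P(success) = sum over x = 5, 6, 7 of P[Bin(7,p) = x] × P[Bin(13,p) ≥ 14 - x]

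At p = 0.50 this is (21/128)(0.1334) + (7/128)(0.2905) + (1/128)(0.5) = 0.0417. At p = 0.80 it is 0.812. The stated alpha of 0.05 and power of 80% are reproduced, so the design is not in error.

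**Worked example (sizes assumed).** Three TILs of 20 mm, baseline sum 60 mm. One grows to 26 mm (+30%, +6 mm) and is withdrawn and treated; the other two are 13 mm at Visit 6.

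| Handling of the withdrawn TIL | Calculation | Change | PR? |
|---|---|---|---|
| Site measured as 0 | 26/60 - 1 | -57% | yes |
| Dropped from both sums | 26/40 - 1 | -35% | yes |
| Carried forward at 26 mm | 52/60 - 1 | -13% | no |

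**General case.** Take k equal TILs, one at +30% and withdrawn. The fall f that each other TIL needs for PR is:

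- measured as 0: f ≥ 1 - 0.7k/(k - 1);
- dropped: f ≥ 0.30;
- carried forward: f ≥ 1 - (0.7k - 1.3)/(k - 1).

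| k | Measured as 0 | Dropped | Carried forward |
|---|---|---|---|
| 2 | none | 30% | 90% |
| 3 | none | 30% | 60% |
| 4 | 7% | 30% | 50% |
| 5 | 12.5% | 30% | 45% |

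Even without the zero reading, the class is open whenever the other lesions fell by an amount between the last two columns.

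**Does Appendix B's PD row settle it?** That row gives overall PD when the TIL entry is PD. With the other TILs stable, the whole sum reaches +20% only if the failing TIL grew by 0.2k: 40%, 60%, 80% or 100% for k = 2 to 5. A single lesion can meet the individual criterion at about 20%. So the row often does not apply at withdrawal.

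**Effect on alpha (share q assumed).** If a share q of true non-responders is counted as PR, p = 0.50 + 0.50q.

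| q | Expected subjects, of 10 non-responders in 20 | p | Exact alpha |
|---|---|---|---|
| 0 | 0 | 0.50 | 0.042 |
| 2% | 0.2 | 0.51 | 0.050 (0.0499) |
| 5% | 0.5 | 0.525 | 0.065 |
| 10% | 1.0 | 0.55 | 0.096 |

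**A second, smaller gap.** PR is measured from baseline, and the second PD limb from nadir. Reading tumor burden as the diameter sum, both are met at Visit 6 when 1.2 × nadir ≤ Visit 6 sum ≤ 0.7 × baseline. That requires nadir ≤ 0.583 × baseline. Example: baseline 40, nadir 20, Visit 6 26 mm gives 26/40 - 1 = -35% and 26/20 - 1 = +30%. On the same reading the 5 mm floor in the first PD limb has no effect: any rise above 20% that satisfies that limb also satisfies the limb of at least 20% over nadir, which has no floor.

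**The case against.** The strongest objection is textual. Section 9.4.1.2 words individual-lesion progression on the sum of the target lesions. Taken literally, a TIL would be withdrawn for size only when the sum had progressed, and Appendix B's PD row would then apply. But the section says it assesses each lesion, and Table 7 lets a subject continue on the remaining TILs, so a per-lesion reading is the evident intent. The point rests on that reading.

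Second, the readings are not equally plausible. Scoring a treated site as 0 is hard to defend, and the fixed baseline sum weighs against dropping a lesion, although the word withdrawn points the other way. This is fair, but dropping and carrying forward still disagree over wide ranges.

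Third, any sum-based PR can include a failed lesion. One of three equal TILs at +30% and two at -60% gives (1.3 + 0.4 + 0.4)/3 - 1 = -30%, a PR with no withdrawal at all. That stands, and carrying forward does not change it. What the missing rule adds is response credited to another therapy or to removal of the failure. The per-lesion response rate among the secondary endpoints shows such failures but does not drive the decision.

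Fourth, a reader might infer that the PR/PD overlap is a proven contradiction between Section 16.1.1 and Appendix B. The documents do not support that. The Appendix B grid takes the TIL category as already assigned. Any overlap subject had earlier been at least 41.7% below baseline, so the best-overall-response sentence can be read as giving PR. That sentence is not named as the Visit 6 definition, so the texts leave the class unsettled.

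**Conclusion.** The gap is real and should be fixed before Visit 6 data are classified. Two careful readers can assign the same multi-TIL subject to different classes, and two of the three readings can count a subject with a failed lesion as a responder.

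Its realised size is unknown: the documents give no rate of multi-TIL subjects or of TIL withdrawals before Visit 6, and single-TIL subjects are not affected. A reader might infer that the trial's alpha is already above 0.05. The documents do not support that. The stated design attains 0.042, the reclassified shares are assumptions, and at 2% alpha is still within 0.05. It passes the limit at the assumed 5% (0.065) and 10% (0.096).

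The PR/PD overlap is a secondary clarification, and its frequency is not estimated.

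**What to change.** For endpoint classification only:

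1. In Section 9.4.1.1, Section 16.1.1 and Appendix B, state that a TIL withdrawn or given non-study treatment before Visit 6 enters all later sums at its last pre-intervention diameter and cannot count as disappeared for CR.
2. Add a sensitivity analysis of ORR that counts every such subject as a non-responder.
3. Define tumor burden, and add one sentence saying which class holds when PR and PD are both met at Visit 6, so that Section 16.1.1, the best-overall-response sentence and the Appendix B grid agree.
4. The sponsor must reconcile the PD passages, including those in Section 9.4.1.2 and Table 7 and the status of the 5 mm floor. No clinical rule is proposed here.

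The cost is a few sentences and one extra analysis. No new data are needed, because target lesions are already measured at each clinic visit. The observed ORR may be slightly lower, since subjects like the -13% example would not count as PR. The design is sensitive in this direction too: if 5% of the responders expected at a true rate of 80% became non-responders (an assumption), p would be 0.76 and power 0.70. A subject whose other TILs shrink enough can still be PR, as under any sum rule; the sensitivity analysis shows how much of the result depends on such subjects.

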16.1.2 Secondary Endpoints

 To assess the safety and adverse effect profile of talimogene laherparepvec in low risk cSCC. Adverse events to be assessed according to National Cancer Institute Common Terminology. This will be determined by incidence of all adverse events (AEs), grade ≥ 3 AEs, safety adverse events (SAEs), and events requiring the discontinuation of study drug, local effects on the tumor (ie, pain, inflammation and ulceration), and any clinically significant laboratory values.

- 2. Time to response in cSCC TILS. Time to response is the time from first visit until objective tumor response (CR or PR) is identified
- 3. Duration of overall response (DOR) of TILs. This will be measured from the time measurement criteria are met for CR or PR (whichever status is recorded first) until the first date that recurrence or progressive disease (PD) is objectively documented, taking as reference for PD the smallest measurements recorded since the treatment started. If no recurrence or PD is documented after PR or CR is observed the time measurement will be performed at Visit 8.
- 4. Durable response rate of TILs. The duration of overall response is ORR lasting continuously for > than or equal to 6 months.
- 5. Time to progression (TTP) of TILs. This will be measured from the time treatment is initiated until the first date that recurrence or progressive disease (PD) is objectively documented, taking as reference for PD the smallest measurements recorded since the treatment started.
- 6. Overall response rate (CR+PR) of TILs assessed by imaging technique (high frequency ultrasound) and correlate it with clinical overall response rate.
- 7. Overall clinical response rate (CR+PR) of individual TILs injected with talimogene laherparepvec (not as overall subject response). Overall response rate is defined as the proportion of injected lesions which achieved complete and partial response.
- 8. Overall clinical response rate (CR+PR) in cSCC TNILs. Overall response rate is defined as the proportion of subjects who achieved complete and partial response in TNILs. cSCC TNILs will be categorized by distance to TILs. Group 1: < 5 cm, Group 2: 5 to 15 cm, Group 3: >15 cm. Response rates in TNILs will be measured using a ruler or calipers. Digital photograph of the lesion will be recorded each visit. Complete response of TNILs will be defined as the disappearance of all TNILs and partial response defined as at least a 30% decrease in the sum of the diameters of TNILs, taking as reference the baseline sum diameters. Progression is defined as 20% increase of at least 5 mm in the sum of the longest diameters of the TNILs compared with the smallest sum of the longest diameter burden). Stable disease (SD) is defined as decrease in tumor size <30% or an increase in size <20% that is less than 5 mm in the sum of the longest diameters of the TNILs compared with the smallest sum of the longest diameters of the TNILs compared with the smallest sum of the longest diameters of the TNILs compared with the smallest sum of the longest diameters of the TNILs compared with the smallest sum of the longest diameters of the TNILs compared with the smallest sum of the longest diameters of the TNILs compared with the smallest sum of the longest diameters of the TNILs compared with the smallest sum of the longest diameters of the TNILs compared with the smallest sum of the longest diameters of the TNILs compared with the smallest sum of the longest diameters of the TNILs compared with the smallest sum of the longest diameters of the TNILs compared with the smallest sum of the longest diameters of the TNILs compared with the smallest sum of the longest diameters of the TNILs compared with the smallest sum of the longest diameter recorded.

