- Inject 0.1ml 4ml (based on TILs size) and number of lesions selected.
 Talimogene laherparepvec at nominal concentration of 10⁸ PFU/mL with approximately 1.15 mL in a 2 mL vial for the subsequent doses.

Visit 4: Fourth injection visit: Two (2) Weeks after V3

- Target lesions are identified and documented with measurements and photographs. Photographs will be taken with global and close up view of the anatomical area and lesion (Appendix A).
- Inject 0.1ml 4ml (based on TILs size) and number of lesions selected.
 Talimogene laherparepvec at nominal concentration of 10⁸ PFU/mL with approximately 1.15 mL in a 2 mL vial for the subsequent doses.

Visit 5: First Follow up visit: Four (4) weeks after V4

 Target lesions are identified and documented with measurements and photographs. Photographs will be taken with global and close up view of the anatomical area and lesion (Appendix A).

Visit 6: Second Follow up visit: Four (4) weeks after V5

 Target lesions are identified and documented with measurements and photographs. Photographs will be taken with global and close up view of the anatomical area and lesion (Appendix A). A repeat high-frequency ultrasound of target lesions will be completed to assess response from baseline.

Visit 7: Third Follow up visit: Six (6) weeks after V6

• Target lesions are identified and documented with measurements and photographs. Photographs will be taken with global and close up view of the

anatomical area and lesion (Appendix A).

Visit 8: Fourth Follow up visit: Fourteen (14) weeks after V7

• Target lesions are identified and documented with measurements and photographs. Photographs will be taken with global and close up view of the anatomical area and lesion (Appendix A).

Visit 9: Telephone Follow up: twelve (12) months after first injection (V1)

• Research coordinator will assess patient over the phone to determine if any changes have occurred to target lesions after V8.

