- Assess for any adverse events
- Skin exam only of target lesions
- Photograph and measure all target lesions (Appendix A)
- Ultrasound of TILs at Radiology Department for follow-up evaluation(Appendix B)
- Schedule the third follow up visit in 6 weeks

Visit 7- Third follow up visit (42 +/- 10 days)

- Vital signs
- Review con meds
- Assess for any adverse events
- Skin exam only of target lesions
- Photograph and measure all target lesions (Appendix A)
- Schedule the next follow up visit in 14 weeks.

Visit 8 - Fourth follow up visit (98 +/- 21 days)

- Vital signs
- Review con meds
- Assess for any adverse events
- Skin exam only of target lesions
- Photograph and measure all target lesions (Appendix A)

Visit 9 – Telephone Follow up (356 +/- 31 days) after Visit 1

- Assess for changes of target lesions
- If active lesion(s) are noted by the participant, they will follow up with a dermatologist and their records will be requested

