9.4.1.1 Tumor Response

Complete Response (CR): Complete disappearance of all TILs (whether measurable or not, and no new lesions at the site of injection) confirmed by an assessment 8 weeks after the end of the injections (Visit 6).

Partial Response (PR): Decrease in tumor burden $\ge 30\%$ relative to baseline confirmed by an assessment 8 weeks after the end of the injections (Visit 6).

Duration of Overall Response (DOR): DOR is when the time measurement criteria are met for CR or PR (whichever status is recorded first) until the first date that recurrence or progressive disease (PD) is objectively documented, taking as reference for PD the smallest measurements recorded since the treatment started. If no recurrence or PD is documented after PR or CR is observed the time measurement will be performed at Visit 6 for PR and Visit 8 for CR.

Durable Response Rate (DRR): Measured from the time measurement criteria are met for CR or PR (whichever status is recorded first) with the response lasting continuously for > than or equal to 6 months. For PD, the reference will be the
smallest measurements recorded since the treatment started.

Time to progression (TTP): This will be measured from the time treatment is initiated until the first date that recurrence or progressive disease (PD) is objectively documented, taking as reference for PD the smallest measurements recorded since the treatment started.

Progressive Disease (PD): Progression is defined as >20% increase of at least 5 mm in the sum of the longest diameters of the target lesions or increase in tumor burden $\ge 20\%$ relative to nadir (minimum recorded tumor burden) or the appearance of one or more new lesions confirmed by an assessment 8 weeks after the end of the injections (Visit 6).

• **Rapid PD (RPD):** Is defined as an increase of >50% in tumor burden for lesions >2 cm in diameter or 100% tumor burden increase for lesion ≤2cm between visits.

Stable Disease (SD): Not meeting criteria for CR or PR, in absence of PD (Decrease of tumor size <30% to increase in size <20% of less than 5 mm in the sum of the longest diameters of the target lesions).

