16.2.2 Safety and Adverse effects of talimogene laherparepvec in cSCC

Summary statistics (counts, percentage, mean, standard deviation, etc.) will be presented for the safety and adverse endpoint as appropriate. Grading of adverse effects will be done as per CTCAE 4.03 grading of the National Cancer Institute.

16.2.3 Duration of overall response (DOR) of TILs.

Once a PR or CR has been established, the analysis will consist of Kaplan-Meier estimates. The analysis will also include a median and a 95% 1-sided exact confidence interval.

16.2.4 Durable Response Rate of TILs.

Once a PR or CR has been established, the analysis will consist of Kaplan-Meier estimates. We will consider durable response when continuously PR or CR is sustained for at least 6 months. The analysis will also include a median and a 95% 1-sided exact confidence interval.

16.2.5 Time to progression (TTP) of TILs.

The analysis of time to response will consist of Kaplan-Meier estimates. The median time and 95% confidence interval will be presented.

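### Duration of response sets no time limit on events but closes recurrence-free responders at Visit 8 (or at Visit 6 for PR in 9.4.1.1), and the plan does not say whether recurrences found through the Visit 9 call count

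*Combined protocol and SAP*

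**What the plan says.** - **Event.** Sections 3.2 (item 3) and 16.1.2 (item 3) start DOR when CR or PR criteria are first met and run it "until the first date that recurrence or progressive disease (PD) is objectively documented". Neither gives a last date for events.
- **Closing a responder without an event.** The same items say "If no recurrence or PD is documented after PR or CR is observed the time measurement will be performed at Visit 8". Section 9.4.1.1 gives a different rule: "the time measurement will be performed at Visit 6 for PR and Visit 8 for CR".
- **Analysis.** Section 16.2.3 says "Once a PR or CR has been established, the analysis will consist of Kaplan-Meier estimates" and adds a median with a one-sided 95% interval. It has no censoring rule. Section 16.2.6 does state one, but for time to response only.
- **After Visit 8.** Section 9.3 has "Visit 9 – Telephone Follow up (356 +/- 31 days) after Visit 1", and Table 1 in 2.4 places the call at twelve months and directs it at changes in the target lesions since Visit 8. Section 9.3 continues: "If active lesion(s) are noted by the participant, they will follow up with a dermatologist and their records will be requested".

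**The concern.** A dermatologist's record of a recurrence after Visit 8 can meet the event definition. A subject who reports no change at the same call gains no follow-up from it, because the closing rule has already ended that subject's time at Visit 8. If such recurrences are counted, everyone at risk after the closing visit is there because the event is known to have happened. Kaplan-Meier needs follow-up to end independently of outcome, and here it would not.

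At stake are the tail of the DOR curve and its median, which 16.2.3 names as a reported summary. With few responders, one late recurrence could yield a median that says nothing about the others. If the rule were chosen after late recurrences had been seen, the choice would also be data-driven.

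The Visit 6 closing point for PR in 9.4.1.1 creates the same problem earlier. Progression found at Visit 7 or 8 would be an event, while PR subjects without progression would have stopped at Visit 6.

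**Working it through.** **Number of responders.** The documents give no figure for DOR, so the Simon design in 16.2.1 sizes the responder set. Its rule is to continue if at least 5 of 7 respond and to succeed if at least 14 of 20 respond. P(X1 ≥ 5 and X1 + X2 ≥ 14) is 0.042 at a 50% response rate and 0.812 at 80%, which agrees with the stated alpha of 0.05 and power of 80%. A successful trial therefore has at least 14 responders, and 16 are expected at 80% (0.8 × 20).

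**Schedule (Table 1, nominal).** The intervals after Visit 1 are 3, 2, 2, 4, 4, 6 and 14 weeks (the last: "Visit 8: Fourth Follow up visit: Fourteen (14) weeks after V7").

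| Visit | V2 | V3 | V4 | V5 | V6 | V7 | V8 |
|---|---|---|---|---|---|---|---|
| Week | 3 | 5 | 7 | 11 | 15 | 21 | 35 |
| Day | 21 | 35 | 49 | 77 | 105 | 147 | 245 |

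Visit 9 is at day 356 ± 31, that is day 325 to 387. Week 52 (day 364) lies in that window.

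**One late recurrence, Visit 8 closing.** Take 14 responders first recorded at Visits 3 to 6. Thirteen stay recurrence-free, and one Visit 6 responder recurs, dated week 52.
- Closed times are 35 minus the response week, so the longest is 35 − 5 = 30 weeks.
- The event time is 52 − 15 = 37 weeks, with one subject at risk. S = 1.00 × (1 − 1/1) = 0.00, and the median is 37 weeks.
- Events and censoring both cut at Visit 8: no event, S = 1.00, median not reached.
- All carried to Visit 9 instead: S = 13/14 = 0.93, median not reached.

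**With earlier events too.** Let all 14 respond at Visit 5, two recur at Visit 7 and one recur on day 356. S is 12/14 = 0.857 after Visit 7, then 0.00 at 356 − 77 = 279 days. Cut at Visit 8 it stays at 0.857. Carried to Visit 9 it is 0.857 × 11/12 = 0.786.

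**When the late event is alone at risk.** For a recurrence on day R in a subject who responded on day a, with b the earliest response day among the others, the condition is R − a > 245 − b, or a − b < R − 245. At R = 356 the limit is 111 days, and the largest spread from Visit 2 to Visit 6 is 105 − 21 = 84 days, so the condition always holds. At R = 325 the limit is 80 days, so it can fail. With response visits assumed uniform over Visits 2 to 6, the curve reaches zero in 100% of simulated cases if the recurrence is dated day 356. The figure is about 98.5% if it is dated across days 325 to 387, and about 67% if it is dated on any day between Visit 8 and day 356.

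**How often.** Assume 14 responders, response at V3/V4/V5/V6 with weights 0.15/0.25/0.30/0.30, and exponential recurrence from Visit 6 at 10% or 20% per year.
- The chance that one responder recurs between weeks 35 and 52 is 0.90^(20/52) − 0.90^(37/52) = 0.0325, or 0.0646 at 20%. The chance of at least one among 14 is 1 − (1 − 0.0325)^14 = 0.37, or 0.61.
- In line with that, the simulated median is reached in 40% or 63% of trials if late recurrences are dated week 52. Common follow-up to Visit 9 gives 4% or 9%.
- If they are dated at onset, the figure is about 30% or a little over 50%.
- Mean S at 26 weeks is 0.97 against 0.97 at 10%, and 0.93 against 0.94 at 20%.

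**PR closed at Visit 6 (9.4.1.1).** Let 14 subjects respond at Visit 5, with one PR progressing at Visit 7, so the event time is 21 − 11 = 10 weeks. PR subjects without progression stop at 15 − 11 = 4 weeks.
- If all 14 are PR, the event is alone at risk and S = 0.
- If 7 are CR, followed to Visit 8, and 7 are PR, 8 are at risk and S = 7/8 = 0.875.
- With one Visit 8 cut-off, 14 are at risk and S = 13/14 = 0.929.

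**The case against.** The strongest reply is that Visit 8 is the end of response assessment. The schedule in section 26 marks tumor evaluation through Visit 8 and gives the telephone contact only a verbal assessment. Section 9.5.1 says participation is complete at Visit 8 if the sites are disease-free. Section 7.4 lets subjects restart systemic interventions after Visit 8. An analyst could reasonably apply Visit 8 to events as well, and the asymmetry after Visit 8 would then vanish.

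This stands as a limit on the claim. A reader might infer that the plan does count Visit 9 recurrences in DOR. The documents do not say so, and a lesion reported only by telephone would not by itself be objectively documented. But they do not exclude such recurrences either, and the records request exists to document them. Treating the Visit 8 closing as censoring is also an inference, since 16.2.3 is silent.

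A reader might also infer that durability is badly understated overall. The figures do not support that: with Visit 8 closing, mean S at 26 weeks, the plan's own 6-month threshold, hardly changes. Nor is a drop to zero certain, because a recurrence dated soon after Visit 8 can fall within other subjects' follow-up. The 40% and 63% figures use the most unfavourable dating.

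A further objection concerns carrying responders to Visit 9. Table 7 has lesions in continuing PR offered alternative treatment at Visit 8. Later event-free time in those subjects cannot simply be credited to the study drug. That stands, and it limits any Visit 9 analysis.

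**Conclusion.** The concern holds as an unspecified and, read literally, asymmetric cut-off, together with a direct conflict between 9.4.1.1 and sections 3.2 and 16.1.2 on the closing visit.

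If recurrences found through Visit 9 count, one of them among about 14 responders can take the DOR curve to zero and create a false median (37 weeks in the example, against not reached). How often depends on assumed recurrence rates, the assumed spread of response visits and the date given to a late recurrence.

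The damage is confined to the tail and median of one secondary endpoint. ORR and the Simon decision are untouched. The reassurance about the 6-month estimate was checked with Visit 8 closing. It does not carry over to the PR rule in 9.4.1.1, under which distortion can begin at Visit 7.

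**What to change.** In 3.2 item 3, 9.4.1.1, 16.1.2 item 3 and 16.2.3, reconcile the closing visit and state one rule before DOR is analysed:

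- DOR events count only through Visit 8.
- Every responder without an event, CR or PR, is censored at the last tumor assessment up to Visit 8.
- Recurrences found through the Visit 9 call or requested records are listed separately, with their dates and source.

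Any sensitivity analysis using Visit 9 should be limited to CR subjects with a completed call and no other treatment of the target lesions. Those without recurrence are censored at the call date.

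The cost is a few sentences in four places, with no new data or visits. The rule does not lengthen follow-up: a response first recorded at Visit 5 or 6 is still observed for only 35 − 11 = 24 or 35 − 15 = 20 weeks by Visit 8, as it is now.
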